### **Individual patient withdrawal**

Patients may voluntarily withdraw from the study for any reason at any time. They may be considered withdrawn if they state an intention to withdraw, fail to return for visits, or become lost to follow-up for any other reason.

If premature withdrawal occurs for any reason, the investigator must make every effort to determine the primary reason for a subject's premature withdrawal from the study and record this information on the Study Completion eCRF.

The subject should be withdrawn from the trial under the following circumstances (but not limited to):

- Withdrawal of informed consent
- New onset of healthy issues
- Pregnancy
- Any other protocol deviation that results in a significant risk to the subject's safety

For patients who are lost to follow-up (i.e., those patients whose status is unclear because they fail to appear for study visits without stating an intention to withdraw), the investigator should document the steps taken to contact the subject, e.g., dates of telephone calls, registered letters.

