## Glossary of terms

Screening	Point/time of subject/patient entry into the study; the point at which informed consent must be obtained (i.e., prior to starting any of the procedures described in the protocol)
Enrollment	Point/time of subject/patient randomisation into the study / assignment of a randomization number.
Investigational drug	The study drug whose properties are being tested in the study; this definition is consistent with US CFR 21 Section 312.3 and is synonymous with "investigational new drug".
Phase	A major subdivision of the study timeline; begins and ends with major study milestones such as, Screening, or Study Completion.
Treatment Period	A minor subdivision of the study timeline that divides phases into smaller functional segments, i.e., the time starting from Baseline prior first study drug administration until the last day prior the next Baseline, or the Study Completion visit.
Premature subject/patient withdrawal	Point/time when the subject exits from the study prior to the planned completion of all study drug administration and assessments. At this time all study drug administration is discontinued. Study Completion assessments must be completed.
Study drug	Any drug administered to the subject as part of the required study procedures; includes investigational drug and any control and comparator drugs.

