## 5.5.6      **Rescue**

### 5.5.6.1    **Rescue of study eye**

For any patients who meet the following criteria in the study eye, the study mug will be discontinued, and conventional therapy instituted:

- Loss of >10 letters in best corrected visual acuity (BCVA) at any visit, as compared to baseline that in the opinion of the investigator is due to worsening of uveitis.
- Active vitritis, anterior chamber inflammation, or chorioretinitis 28 ± 3 days after their last dose that, in the opinion of the investigator, is significantly worse as compared to the previous visit and requires alternate therapy
- Unilateral flare in fellow / non-study eye which does not respond to local treatment (including ozurdex® implant) or bilateral flare in both eyes which require the intensification of systemic immunosuppressive therapy.

Patients who are rescued will be asked to attend the per protocol visit schedule for the remainder of the trial in order to be followed up for safety.

Corporate Confidential Information

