### 5.5.6.3 Recommended treatment of adverse events

Ocular adverse events should be treated according to the type of adverse event. For clinically significant acute elevation of intraocular pressure (IOP) following LFG316 injection, anterior chamber paracentesis should be performed and normalization of IOP verified. For sub-acute or persistent elevation in IOP, aqueous suppressants may be indicated. Iritis or vitritis should be treated in accordance with permitted medications (see below). Endophthalmitis should be treated with vitreous paracentesis and culture and/or vitrectomy, as indicated, plus appropriate IVT antibiotics per local practice.

**NOTE:** In case of an adverse event attributed to IVT LFG316, the investigator may wish to remove the LFG316 by pars plana vitrectomy.

With any biologic treatment, systemic hypersensitivity reactions are theoretically possible. These can manifest with itching, flushing, headache, nausea/vomiting, hypotension, urticaria, bronchospasm, or angioedema. Assess and treat for anaphylaxis if indicated, and initiate supportive care. Fluids, vasopressors, corticosteroids, antihistamines, bronchodilators, and oxygen should be on hand.

Patients may remain in the study even after receiving treatment for adverse events.

Medication used to treat AEs must be recorded on the Concomitant medications/Significant non-drug therapies eCRF page after the start of study drug.

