## 6 Visit schedule and assessments

The timing of assessments required during the study is delineated in the [Assessment schedule](#). All data obtained from these assessments must be supported in the subject's source documentation. Source documentation must be available for all data collected during the study and a source documentation verification list provided.

Should it become necessary to repeat an evaluation, the results of the repeat evaluation should be captured.

Patients should be seen for all visits on the designated day with an allowed "visit window" as indicated in the [Assessment schedule](#), or as close to it as possible.

Patients enrolled in the study who discontinue LFG316 treatment prior to Day 85 should attend all remaining study visits in accordance with the protocol.

Corporate Confidential Information

All baseline assessments must be completed prior to LFG316 administration.

Minor deviations for the following post-dose assessment times (~10-15 minutes) during baseline/Day 1 visit are acceptable based on logistical and operational considerations:

- Vitals signs and body measurements during Baseline/Day 1 visit
- Ocular assessments during Baseline/Day 1 visit
- 4 hours Post-injection PK/PD blood collection (if applicable)

There is no strict requirement on the time of day when patients need to return for their outpatient follow up visits.

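### Protocol 5.5.10 tells sites to withdraw from the trial a patient with any new health issue, although Section 6 keeps patients who stop LFG316 on the visit schedule; the effect is small, and 5.5.8 must be aligned for the fix to work

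*Protocol*

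**What the plan says.** Protocol Section 5.5.10, under individual patient withdrawal, opens its list with "The subject should be withdrawn from the trial under the following circumstances". The list is stated not to be exhaustive. Its second bullet is "New onset of healthy issues". That bullet sets no condition on severity, seriousness, relatedness or risk. The last bullet does refer to risk: "Any other protocol deviation that results in a significant risk" to the subject's safety.

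The glossary entry for premature withdrawal reads "Point/time when the subject exits from the study prior to the planned completion of all study drug administration and assessments". It adds that all dosing stops at that point and that "Study Completion assessments must be completed".

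Other parts of the protocol keep comparable patients under observation:

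- Section 6: "Patients enrolled in the study who discontinue LFG316 treatment prior to Day 85 should attend all remaining study visits".
- Section 5.5.6.3: "Patients may remain in the study even after receiving treatment for adverse events".
- Section 5.5.6.1: "Patients who are rescued will be asked to attend the per protocol visit schedule" for the rest of the trial, for safety.
- Section 5.5.10, study stopping criteria: if dosing stops for the whole study, enrolled subjects may stay for observation.
- Section 7.1: permanently stopping study drug is a listed action for an adverse event, leaving the trial is not, and events are to be reassessed at each visit.

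One rule points the other way. Section 5.5.8 says that a patient who needs a prohibited treatment should be withdrawn from the study.

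**The concern.** Section 7.1 defines an adverse event as any new or worsened undesirable sign, symptom or condition. Almost every adverse event is therefore also a new health issue. A site with such a patient finds one section saying to end participation and another saying to stop the drug and continue the visits. Section 11 permits no authorized deviations, so the investigator cannot settle the matter by asking the sponsor for an exception.

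The primary endpoint is assessed at Day 85, which Section 3.3 justifies as the point after the full three-dose course. A patient who leaves earlier has only an exit evaluation. SAP 7.1 classes a patient with none of the response parameters as missing, and SAP 7.4 imputes nothing. Depending on how the exit visit is mapped, the patient either drops out of the denominator or is scored before the course is complete. The remaining scheduled safety visits are lost in both cases.

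**Working it through.** No figure in the plan bears directly on this point. The check is first textual, then a sizing.

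**1. Do the sections conflict?**

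| Source | What it governs | Instruction |
|---|---|---|
| 5.5.10, new health issues | participation in the trial | should be withdrawn |
| Glossary | meaning of withdrawal | exit before assessments are complete |
| Section 6 | patients who stop LFG316 early | should attend all remaining visits |
| 5.5.6.1 | rescued patients | asked to keep the visit schedule |
| 5.5.6.3 | patients treated for an adverse event | may remain |
| 7.1 | action on an adverse event | stopping drug is listed; reassess at each visit |
| 5.5.8 | need for a prohibited treatment | should be withdrawn |

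The clearest conflict is with Section 6. Section 5.5.6.3 is permissive, and the tension with 7.1 is by implication only.

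**2. How many patients?** The documents give no rate for uveitis. Assumption: the earlier intravitreal studies in macular degeneration (Section 1.1) carry over.

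- Three-dose study: no adverse event led to discontinuation among 30 LFG316 patients. One-sided 95% upper limit: 1 - 0.05^(1/30) = 9.5%; × 16 = 1.5 patients.
- Adding the single-dose study (24 patients, no discontinuations): 1 - 0.05^(1/54) = 5.4%; × 16 = 0.9.
- 18-month geographic atrophy study: at least 2 of 150 (1.3%) discontinued for choroidal neovascularization in the study eye. The arm is not stated. If both were among the roughly 100 LFG316 patients (150 × 2/3), the rate is 2.0%; × 16 = 0.3.

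This gives about 0 to 1 of 16, with 2 as an outer bound.

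**3. Effect on the rate if withdrawn patients are scored missing.** The starting point is 11 of 16, the count named in the synopsis sample-size paragraph, used only as an illustration. Exact 90% limits are Beta(0.05; x, n-x+1) and Beta(0.95; x+1, n-x).

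| Case | Rate | Exact 90% CI | Shift (points) |
|---|---|---|---|
| No withdrawal, 11/16 | 68.8% | 45.2-86.8% | – |
| One non-responder lost, 11/15 | 73.3% | 48.9-90.3% | +4.6 |
| One lost, half as likely to respond, (11 - 0.344)/15 | 71.0% | – | +2.3 |
| One responder lost, 10/15 | 66.7% | 42.3-85.8% | -2.1 |
| Two non-responders lost, 11/14 | 78.6% | 53.4-93.9% | +9.8 |
| Two responders lost, 9/14 | 64.3% | 39.0-84.7% | -4.5 |

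Here 0.344 = 0.5 × 11/16. A lost patient as likely to respond as the rest gives no expected shift.

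**4. Effect if the exit visit is scored as Day 85.** Each patient whose status would have differed at Day 85 moves the rate by 1/16 = 6.3 points, either way (10/16 = 62.5%, 12/16 = 75.0%). As an example, an exit on Day 29 precedes the third dose on Day 57. For a patient on the standard oral taper it also falls on the first day of week 5, when 17% of the baseline dose is still due (0.17 × 60 mg = about 10 mg/day).

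**5. Safety window.** Section 7.2 requires SAE reporting regardless of causality until 30 days after participation stops. For a Day 29 exit this ends on Day 29 + 30 = 59. For a patient who finishes at Day 85 it ends on Day 85 + 30 = 115, which is 56 days later.

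**6. Would changing 5.5.10 alone be enough?** No. The geographic atrophy cases suggest that a new non-uveitic condition in the study eye is the likeliest way to meet this bullet, because worsening uveitis goes to rescue. Table 5-1 prohibits, in the study eye, other intravitreal medication, other antibodies, laser, surgery, and new topical, periocular or intravitreal steroid. A patient who needs one of these is withdrawn under 5.5.8 whatever 5.5.10 says.

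**The case against.** **A safety reading was meant.** The list closes with a bullet about significant safety risk, the noun is garbled, and conjunctival haemorrhage is an expected, very common event. Withdrawing for every new issue would empty the trial. This stands as to intent: a reader might infer that nearly every adverse event will end participation, and the documents do not support that as the plan. It does not repair the bullet, which carries no such limit.

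**There is no true conflict, because Section 6 concerns stopping drug and 5.5.10 concerns leaving the trial.** The section title does separate the two. But the bullet sends to withdrawal the same patients for whom 7.1 offers stopping drug, so a site still has to choose.

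**Retention is not the protocol's uniform practice.** This stands. Section 5.5.8 withdraws patients who need prohibited treatment, and it governs much of the study-eye case. Retained Day 85 data from patients treated in this way would also add little to efficacy. Deviation code M01 removes users of prohibited medication from Efficacy 2, and Efficacy 1, the set of primary interest, may count them only up to discontinuation.

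**Little safety information is lost.** Largely true. Exit evaluations are mandatory, adverse events are followed to resolution, SAEs are reported for 30 days, and later ones are reported if causality is suspected. The scheduled visits are still lost.

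**The scoring rules may be settled elsewhere.** This stands. The schedule labels the Day 85 column as visit 9 or 777, so the exit visit may belong there. The mapping, and what discontinuing means in Efficacy 1, may be in Module 8 or in redacted text. A reader might infer that the plan fails to define them; the visible documents cannot show that.

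**Conclusion.** The point holds as a wording conflict that is worth correcting. Taken literally, 5.5.10 removes from the trial patients whom Section 6 would keep on the visit schedule. Each of them loses the true Day 85 assessment and the later scheduled safety visits.

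The effect is probably small: about 0 to 1 of 16 LFG316 patients. This rests on the assumption that discontinuation in the macular degeneration studies is a fair guide. Those studies differ in disease and, for the neovascularization cases, in duration; nor is it stated whether those two patients left the study or only stopped drug.

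A reader might infer that the response rate is biased upward. The documents do not support this. The shift is upward only if the lost patients respond less often than the others, and nothing says that they would. Every shift computed above lies inside the 90% interval around 11/16, and SAP 7.1 says that no decision should rest on the p-value. The conclusion of the trial is not in doubt on this ground. The case for acting is that the correction costs almost nothing.

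**What to change.** In protocol 5.5.10, limit the bullet to new conditions that make continued participation, and not only further dosing, unsafe. For any other new health issue, allow study drug to be stopped and have the patient attend all scheduled visits through Day 85, as Section 6 already provides, unless consent is withdrawn.

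In the same amendment, align 5.5.8: a patient who needs a prohibited treatment stops study drug but stays for the scheduled visits, as 5.5.6 already arranges for rescued patients. Without this, the change does not reach new study-eye conditions that need such treatment. For these patients the gain is mainly in safety data, for the reason given above.

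The cost is a short written amendment under Section 11.1. The visits are already in the schedule, so no new visit or procedure is needed.

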#### **5.5.11 Emergency unblinding of treatment assignment**

Not applicable. Both patient and investigator are aware of treatment assignment.

#### **5.5.12 Study completion and post-study treatment**

Each patient will be required to complete the study in its entirety, and thereafter no further study treatment will be made available to them. The study will complete when the last subject completes his/her Study Completion visit, and any repeat assessments associated with this visit have been documented and followed-up appropriately by the investigator.

##### **5.5.12.1 Early study termination**

The study can be terminated at any time for any reason by Novartis. Should this be necessary, study patients should be seen as soon as possible and treated as described in [Section 5.5.10](#) for a prematurely withdrawn subject. The investigator may be informed of additional procedures to be followed in order to ensure that adequate consideration is given to the protection of the subject's interests. The investigator will be responsible for informing IRBs and/or ECs of the early termination of the trial.

## 6 Visit schedule and assessments

The timing of assessments required during the study is delineated in the [Assessment schedule](#). All data obtained from these assessments must be supported in the subject's source documentation. Source documentation must be available for all data collected during the study and a source documentation verification list provided.

Should it become necessary to repeat an evaluation, the results of the repeat evaluation should be captured.

Patients should be seen for all visits on the designated day with an allowed "visit window" as indicated in the [Assessment schedule](#), or as close to it as possible.

Patients enrolled in the study who discontinue LFG316 treatment prior to Day 85 should attend all remaining study visits in accordance with the protocol.

Corporate Confidential Information

All baseline assessments must be completed prior to LFG316 administration.

Minor deviations for the following post-dose assessment times (~10-15 minutes) during baseline/Day 1 visit are acceptable based on logistical and operational considerations:

- Vitals signs and body measurements during Baseline/Day 1 visit
- Ocular assessments during Baseline/Day 1 visit
- 4 hours Post-injection PK/PD blood collection (if applicable)

There is no strict requirement on the time of day when patients need to return for their outpatient follow up visits.

### 6.1 Dietary, fluid and other restrictions

None.

### 6.2 Patient demographics/other baseline characteristics

#### Demographics

Date of birth, sex, race, and predominant ethnicity will be collected.

#### Relevant medical history/ Current medical conditions

Relevant medical history and current medical conditions will be recorded on the in the eCRF until the start of the study drug.

History of surgical sterilization and postmenopausal status needs to be captured under relevant medical history page in the eCRF. Any event or change in the subject's condition or health status occurring **prior to** the initial study drug administration will be reported in the Relevant medical history/Current medical conditions section of the eCRF.

**Ocular and uveitis history**

Past or concurrent ocular history and history of uveitis diagnosis, progression, and treatments will be captured in the eCRF.

**Smoking history**

Smoking history will be recorded in the eCRF.

**6.3 Treatment exposure and compliance**

Patient compliance, based on the completion of the IVT injection, will be evaluated by the study investigator.

**Drug administration record**

All doses prescribed and dispensed to the subject must be recorded on the Dosage Administration Record.

Date and time of dose administration, including the start time of the IVT injection, will be recorded in the Dosage administration record section of the eCRFs.

**Study completion information**

Information on the date the subject last received the study drug, the subject completion or discontinuation of the study and the reason for discontinuation of the study will be recorded on the Study Completion eCRF page.

Study Completion evaluations must also be performed when a subject prematurely withdraws from the study for whatever reason.

**Comments**

All comments related to study conduct will be added to the eCRF.

## 6.4 Efficacy / Pharmacodynamic assessment

### 6.4.1 Vitreous haze

Vitreous haze in the study eye will be measured by the Nussenblatt scale, as described below.

**Table 6-1 Vitreous haze scoring**

Grade 0	No haze
Trace	Slight blurring of optic disc margin
Grade 1+	Slightly blurred optic nerve and vessels
Grade 2+	Moderately blurred optic nerve and vessels
Grade 3+	Optic nerve head border blurry but visible
Grade 4+	Optic nerve head obscured

### 6.4.2 Anterior Chamber cells

Anterior chamber cells will be scored as per SUN criteria (Jabs et al 2005) described below:

**Table 6-2 Anterior chamber cell grading**

Grade Description	Aqueous Cells
0	1 cell
0.5	1-5 cells
1	6-15 cells
2	16-25 cells
3	26-50 cells
4	> 50 cells

### 6.4.3 Chorioretinal lesions

Chorioretinal lesions will be assessed as present or absent by the investigator

Corporate Confidential Information

### 6.4.6 Visual acuity

Visual acuity in the study eye will be measured as described in [Section 6.5.9.2](#) this protocol.

### 6.4.7 Optical coherence tomography(sd-OCT)

Spectral domain optical coherence tomography will be performed on both eyes for each patient according to the [Assessment schedule](#). sd-OCT images will be transferred according to the imaging manual or as directed by the sponsor.

**6.4.8 Total CS**

Corporate Confidential Information

**6.4.8.1 Total CS sample collection and processing**

Corporate Confidential Information

**6.4.8.2 Total CS analytical method**

Corporate Confidential Information

**6.5 Safety****6.5.1 Physical examination**

Physical examination may be performed by the investigator or by the patient's primary care provider, if properly source-documented. A physical exam performed within 4 weeks of the appointed date will suffice, unless the patient's medical history has changed in the interim.

A complete physical examination will include the examination of general appearance, skin, neck (including thyroid), eyes, ears, nose, throat, lungs, heart, abdomen, back, lymph nodes, extremities, vascular system and neurological system. If indicated based on medical history and/or symptoms, rectal, external genitalia, breast, and/or pelvic exams may be performed.

Information for all physical examinations must be included in the source documentation at the study site and will not be recorded on the eCRF. Significant findings that are present prior

to the start of study drug must be included in the Relevant Medical History/Current Medical Conditions screen on the subject's eCRF. Significant findings made after the start of study drug which meet the definition of an Adverse Event must be recorded on the Adverse Event screen of the subject's eCRF.

### **6.5.2 Vital signs**

For the purpose of this study, vital signs will include blood pressure and pulse measurements, and rectal or oral body temperature. Systolic and diastolic blood pressure and pulse rate will be assessed after the subject has rested quietly in the sitting position for at least 3 minutes.

### **6.5.3 Height and weight**

Height in centimeters (cm) and body weight (to the nearest 0.1 kilogram [kg] in indoor clothing, but without shoes) will be measured.

